## Appendix 2. Criteria for Dose Limiting Toxicity

### Adverse Events

Unless incontrovertibly due to extraneous causes, treatment emergent events conforming to the following criteria will constitute dose limiting toxicity:

1. Laboratory, vital sign or electrocardiogram findings conforming to the criteria provided below;
2. When not covered by the criteria listed below, treatment emergent adverse event graded as severe or  $\geq$  Grade 3 under the NIAID Division of Microbiology and Infectious Diseases Adult Toxicity Tables (2007 Draft Version).

### Hematology

Hemoglobin	<0.8 times the LLN or <80% times the baseline value if the baseline result is less than the lower limit of the reference range
Hematocrit	<0.8 times the LLN or <80% times the baseline value if the baseline result is less than the lower limit of the reference range
Platelets	<100,000 or $\leq$ 0.77 times the baseline value if the baseline result is less than the lower limit of the reference range.

### Chemistry

Total bilirubin	>1.5 times the ULN
Direct bilirubin	>1.5 times the ULN
Indirect bilirubin	>1.5 times the ULN
Creatinine kinase	>2.0 times the ULN
Creatinine	>1.3 times the ULN

### Coagulation Pathway

PT	$\geq$ 4 seconds above the baseline value
Cardiac Troponin I	If values are normal at baseline, any results above the myocardial ischemia range  Any result in the myocardial infarction range, regardless of baseline values

Fibrinogen  $\leq 0.5$  times LLN or  $\leq 0.5$  times the baseline value

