### 1.3.2. Study Rationale

The clinical investigation of PF-06741086 will continue with study B7841002, an open-label, Phase 1b/2, multiple ascending dose (MAD) study in severe hemophilia A or B subjects, including subjects with inhibitors to factor VIII or factor IX. The clinical risk/benefit profile for this population is considered appropriate for the evaluation of safety, tolerability, PK, PD, and efficacy of multiple doses of PF-06741086. Frequency of bleeding episodes (of study subjects during treatment with PF-06741086) will be compared against the frequency of bleeding episodes in an external control group as a measure of therapeutic efficacy.

The primary objective of study B7841002 is to evaluate the safety and tolerability of multiple ascending doses of PF-06741086 administered by the SC or IV route. Secondary objectives include evaluating the PK and PD properties of PF-06741086, as well as assessing clinical efficacy based on the frequency of bleeding episodes. Selection of the PD endpoints and sampling schedule are based on results from non-clinical studies and the Phase 1 FIH study results. They will reflect either target binding by PF-06741086 (ie, TFPI level) or downstream pharmacologic effects of TFPI inhibition (ie, dPT, TGA, PF1+2 and D-dimer). Thrombosis is a potential risk for inhibition of TFPI, and PF-06741086 is expected to significantly inhibit TFPI, particularly at the highest dose levels. To minimize this risk, hemophilia patients with a known history of thrombotic, ischemic or coronary artery disease, or known pro-thrombotic conditions (eg, Protein C deficiency) will be excluded from this study. Safety monitoring will include laboratory parameters that may be modulated due to coagulopathy (eg, [PT]/INR, aPTT, fibrinogen, ATIII and platelet counts) and parameters to screen for possible thrombotic events (eg, cardiac troponin I). Laboratory endpoints to detect excessive modulation of the coagulation pathway will be monitored during the period of peak drug exposure, until at least 28 days have passed since the final administration.

Potential risks for treatment with PF-06741086 are thrombi or emboli. Depending on location and severity, thrombi or emboli may be life threatening or fatal. An additional potential risk for treatment with PF-06741086 is ADA-induced hypersensitivity.

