### 3.3. Dose Escalation and Stopping Rules

Dose escalation stopping rules will be used to determine whether the maximum tolerated dose has been attained.

Dose escalation will not occur if 2 or more dose-limiting toxicities are met within a dosing cohort of 6 subjects. Dose escalation may occur if  $\leq 1$  dose limiting toxicity is observed within a dosing cohort of 6 subjects. Dose limiting toxicities are defined as:

- Treatment emergent laboratory abnormality as specified in [Appendix 2](#);
- Treatment emergent vital sign abnormality as specified in [Appendix 2](#);
- Treatment emergent ECG abnormality as specified in [Appendix 2](#);
- Treatment emergent severe or  $\geq$  Grade 3 adverse event, as graded by the NIAID DMID criteria for severity unless incontrovertibly due to extraneous causes.

Additional rules governing dose escalation are as follows:

- Dosing at the current dose level (or higher dose levels) will be suspended for any treatment emergent thrombotic event (see [Appendix 1](#) for qualifying AEs) in a subject receiving PF-06741086 to permit characterization of the respective event and communication to regulatory agencies where required. Vessel occlusion related to the insertion or presence of a central venous catheter may be excluded from this criterion after review of the AE with the respective investigator to assess causality and/or clinical significance.
- All treatment emergent adverse events, regardless of system organ class, severity/grade, causality, and/or attribution to treatment with PF-06741086 are assessed and it is determined by the Sponsor that the limit of safety and/or tolerability has been reached.
- Dose escalation will be paused for any treatment emergent serious adverse event (SAE) that occurs in a subject receiving PF-06741086 until causality is fully assessed by the Sponsor. Dose escalation will cease if the SAE is determined to be either drug-related or unknown, and may resume if the SAE is determined to be not drug-related by the Sponsor.

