### **Dose Modifications**

Any subject who experiences a dose limiting toxicity (per [Appendix 2](#)) will be discontinued from treatment with the investigational product and will be followed for adverse event monitoring until resolution of the respective toxicity and elimination of study drug or the end of the study (Day 113) and resolution or stabilization of the respective toxicity, whichever occurs first. In addition, subjects who have not experienced dose limiting toxicities but are currently receiving a dose that met the dose limiting toxicities criteria for termination of dose escalation as defined in [Section 3.3](#) will be removed from the current dose level and dropped to the next lowest exposure level.

Subjects who have not experienced a dose-limiting toxicity may also require dose modifications. Criteria for modifications of dosing in an individual subject are as follows:

- Moderate severity infusion/injection site reactions at more than 2 consecutive visits (eg, Day 22, Day 29, and Day 36);
- Treatment emergent adverse event(s) that increases in severity/grade, without resolution, (eg, Mild to Moderate and continuing) after repeat administration of PF-06741086;

- Treatment emergent adverse event(s) of any severity with more than 2 occurrences following repeat administration of PF-06741086.

Any subject who meets the above criteria during treatment with PF-06741086 will be removed from the current dose level and dropped to the next lowest exposure level, unless the event(s) are incontrovertibly due to extraneous causes or are incontrovertibly complications of hemophilia (see [Section 8.6](#) for qualifying events).

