**Table 6. Blood Volume for SC Cohorts**

Sample Type	Sample Volume (mL)	Number of Sampling Times			Total Volume (mL)
		Screening	Study Period	Follow-Up	
Safety Labs					157
Serum chemistry (with Lipid profile a )	5	1	7	1	45
Hematology	3	1	7	1	27
Prothrombin 20210 mutation	3	1	0	0	3
Factor V Leiden mutation testing	3.5	1	0	0	3.5
aPTT, PT/INR, Anti-thrombin III b , Factor VIII and Factor IX activity c , Fibrinogen, Protein C a , Protein S a , D-dimer, PF1+2 (PD samples) [Single combined sample]	4.5	1	11	1	58.5
Serology (HBs Ag, HBc Ab, HCV Ab, and HIV)	5	1	0	0	5
Cardiac Troponin I d	3	0	5	0	15
PK	4.5	0	11	1	54
Immunogenicity (ADA, NAb)	9	0	5	1	54
PD (note some PD assayed from safety samples)					106.8
TFPI level	2.7	0	11	1	32.4
TGA	3.5	0	11	1	42
dPT	2.7	0	11	1	32.4
Factor VIII and Factor IX inhibitor a	4.5	1	0	0	4.5
CCI [REDACTED]	[REDACTED]	[REDACTED]	[REDACTED]	[REDACTED]	[REDACTED]
Banked biospecimens	4	0	1	0	4
TOTAL					393.8

a at Screening only.

b at Screening and Days 1, 8, 15, 22 and 29 only.

c at Screening and Day 1 only.

d at Days 1, 8, 15, 22 and 29 only.

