6.5.2. Laboratory Data

Laboratory data (including total globulin, PT/INR, aPTT, fibrinogen, anti-thrombin III and cardiac troponin I) will be listed and summarized by dose level and cohort in accordance with the sponsor reporting standards. Baseline is as defined in Section 3.1.2. In addition, laboratory parameters identified in the appendix 2 of the study protocol will be summarized categorically against criteria specified in that appendix. The respective assessments will take into account whether each subject's baseline test result is within or outside the laboratory

reference range for the particular laboratory parameter. Two sets of summaries will be generated: one for subjects with normal baseline value and one for subjects with abnormal baseline value.

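### The Appendix 2 troponin criterion, as worded, does not count a new rise from normal into the myocardial ischemia range

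*Protocol*

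**What the plan says.** Protocol Appendix 2 (Coagulation Pathway) gives two troponin I criteria:

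- Line 1: "If values are normal at baseline, any results above the myocardial ischemia range"
- Line 2: "Any result in the myocardial infarction range, regardless of baseline values"

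SAP Appendix 2 repeats both lines. Neither document gives numeric limits for the two ranges.

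Three rules depend on this text:

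- **DLT definition.** Protocol Section 3.3 lists, as its first type of DLT, "Treatment emergent laboratory abnormality as specified in" Appendix 2. The cohort rule is: "Dose escalation will not occur if 2 or more dose-limiting toxicities are met within a dosing cohort of 6 subjects".
- **Individual subjects.** Under Dose Modifications in Section 3.3, a subject with an Appendix 2 DLT "will be discontinued from treatment with the investigational product".
- **Reporting.** SAP Section 6.5.2 states that "laboratory parameters identified in the appendix 2 of the study protocol will be summarized categorically against criteria specified in that appendix".

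Troponin I is drawn "at Days 1, 8, 15, 22 and 29 only" (Protocol Table 6, footnote d; Table 7 has the same footnote). Section 6.2.1 places the Day 1 draw before dosing.

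**The concern.** A value inside the ischemia range is not above it, and it is not in the infarction range. Read as written, a subject with normal troponin at baseline and an ischemia-range value on treatment therefore satisfies neither line. Yet a condition restricted to normal baselines makes most sense if it was meant to catch exactly this new, lower-level rise.

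The analyte matters here. Protocol Section 1.3.2 names thrombi and emboli as potential risks that may be life-threatening or fatal, and gives troponin I as its example of a laboratory screen for thrombotic events. Section 9.8 provides no data monitoring committee, so the written thresholds carry much of the weight in escalation decisions. An objective laboratory trigger should not need a separate adverse-event report or diagnosis before it acts.

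**Working it through.** The plan states no figure on this point, so there is none to reproduce. The check is a logical one, followed by simple counts.

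**1. Apply both lines to every combination.** Assume contiguous, non-overlapping bands in the order normal, ischemia, infarction. Cross baseline (normal or not normal) with the on-treatment result.

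| Baseline | Result | Line 1 as written | Line 2 | DLT as written | DLT with 'in or above' |
|---|---|---|---|---|---|
| Normal | Normal | No | No | No | No |
| Normal | Ischemia | No | No | **No** | **Yes** |
| Normal | Infarction | Yes | Yes | Yes | Yes |
| Not normal | Normal | No | No | No | No |
| Not normal | Ischemia | No | No | No | No |
| Not normal | Infarction | No | Yes | Yes | Yes |

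Line 2 alone counts 2 of 6 combinations, and both lines together count the same 2. Line 1 adds no case. With 'in or above' the count is 3 of 6, and the one added combination is a normal baseline with an ischemia-range result.

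**2. Does the gap depend on the assumed bands?**

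- If there is a gap between the ischemia and infarction bands, line 1 does catch values in that gap, so it is no longer redundant. A value inside the ischemia band is still missed.
- If the bands partly overlap, the part of the ischemia band outside the overlap is still missed.
- Only an ischemia band lying wholly inside the infarction band closes the gap, and two named ranges would then serve little purpose.

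So contiguity is needed for the redundancy result but not for the gap.

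**3. How many values does the wording govern?** Day 1 is pre-dose, which leaves Days 8, 15, 22 and 29: 4 scheduled values per subject, 4 × 6 = 24 per cohort and 4 × 24 = 96 in the planned 24 subjects. These count draws, not expected events.

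**4. What happens under the escalation rule?** Suppose 2 of 6 subjects have such a rise and nothing else. As written, laboratory DLTs = 0 and the DLT rule permits escalation. As reworded, laboratory DLTs = 2 and escalation is barred.

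**5. How often might the rewording bar escalation?** Let s be the chance that a subject has an isolated ischemia-range rise. The documents give no rate, so s is assumed. With independent subjects and no other DLTs, the chance of two or more in 6 is 1 − (1 − s)^6 − 6s(1 − s)^5.

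| s (assumed) | As written | Reworded |
|---|---|---|
| 0.02 | 0 | 0.0057 |
| 0.05 | 0 | 0.0328 |
| 0.10 | 0 | 0.1143 |
| 0.20 | 0 | 0.345 |

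If each subject also has an assumed, independent 10% chance of some other DLT, the per-subject probability after rewording is 1 − 0.9(1 − s). For s = 0.05 and 0.10, the chance of barring escalation goes from 0.114 as written to 0.212 and 0.320.

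**The case against.** The strongest reply is that this is loose wording, not a real gap. The two lines together suggest two tiers: a lower trigger when baseline was normal, and infarction level otherwise. A sensible reader might take the first line to mean above the ischemia threshold. That is probably what was intended, but it supports the change: on that reading, rewording alters nothing intended and ensures that sites, sponsor and programmers apply the same rule.

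The second reply is that other safeguards exist, some of them stricter than the two-in-six rule:

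- Under Protocol Section 3.3, one serious adverse event pauses escalation, and one event from the Appendix 1 list, which includes myocardial ischaemia, suspends dosing.
- Sections 8.3.1 and 8.15.2 require expedited reporting of suspected thrombotic and ischemic events.
- Section 8.5 makes a test result an adverse event if it needs further diagnostic work or if the investigator or sponsor considers it one.
- Section 3.3 requires sponsor review of safety data through Day 29 in all 6 subjects before progression to a higher dose not already assessed as safe. Every scheduled troponin draw falls within that period.
- SAP Section 6.5.2 still lists and summarizes every troponin value.

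All of this stands, and it means the value would not be invisible. But each route that can stop or pause dosing first needs a report, a diagnosis or a judgement. Under Section 8.5, merely repeating an abnormal test is not an adverse event, and the table of triggered actions in Section 7.8 omits troponin. None of these routes makes an isolated value a laboratory DLT.

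The third reply is that the rewording has a price: each added DLT discontinues a subject, and two drop the remaining subjects on that dose to the next lowest exposure level. That is correct and should be weighed. It is small if such rises are rare, but not if they are common.

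**Conclusion.** The concern holds. Under the text of both appendices, a new rise from normal into the ischemia range is not a laboratory DLT, does not trigger discontinuation and is not counted in the categorical summary. This is true for every band layout except an ischemia range wholly inside the infarction range. The further result, that line 1 is redundant (2 of 6 combinations with or without it), does assume contiguous bands.

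The size is one combination out of six, and a possible change from 0 to 2 counted DLTs in a cohort where two subjects have only this abnormality. How often that would happen cannot be derived from the documents. This is a wording defect in a decision threshold with partial backstops, not evidence that a clinical event would go unseen. It should be fixed. Confidence is medium because the cut-offs are not given and a looser reading is possible.

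**What to change.** In the first troponin line of both Protocol Appendix 2 and SAP Appendix 2, replace 'above' with 'in or above'. Leave the second line unchanged. Stating the central laboratory's cut-offs for the two ranges would help consistent application, but the correction does not depend on it.

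The drafting cost is one line in each document. The operating cost is a possible increase in counted DLTs, with the discontinuations and dose reductions that follow: on the assumed rates above, a 0.6%, 3.3% or 11.4% chance of barring escalation in a cohort of 6 when 2%, 5% or 10% of subjects have such a rise and no other DLT occurs. If the sponsor intended ischemia-range rises not to count, it should say so and delete or redefine the first line, which with contiguous bands has no effect at present.

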**Vital Signs**

Temperature  $> 38.5^{\circ}\text{C}$

Pulse Rate  $< 40$  or  $> 120$  BPM

Blood Pressure  
Systolic  $\geq 30$  mm Hg change from baseline in same posture  
Systolic  $< 90$  mm Hg  
Diastolic  $\geq 20$  mm Hg change from baseline in same posture  
Diastolic  $< 50$  mm Hg

**Electrocardiogram**

PR interval  $\geq 300$  msec  
 $\geq 1.25$  times baseline when baseline  $> 200$  msec  
 $\geq 1.50$  times baseline when baseline  $\leq 200$  msec

QRS interval  $\geq 140$  msec  
 $\geq 1.50$  times baseline

QTcF interval  $\geq 500$  msec

1. VERSION HISTORY

This Statistical Analysis Plan (SAP) for study B7841002 is based on the protocol amendment 4 dated 02Oct2016.

Table 1. Summary of Major Changes in SAP Amendments

SAP Version	Change	Rationale
1	Not Applicable	Original Version
2	
Section 2.1.1 and 2.2: editorial changes
 
Section 3.1.2 and 6.5.2: removed reference to albumin: total globulin ratio.
 
Section 5.2.1 and 6.2.1.1: added presentation of model based ABR and its 80%CI, added SAS codes for generating these estimates.
 
Section 6.1, 6.2 and 6.5.1: Added summary by dose level and hemophilia type
 
Section 6.2: added Wilcoxon rank sum test for ABR
 
Section 6.4.2: changed summary of subject evaluation to by analysis set.
 
Section 6.5.7: added definition and summary of clinical relevant NAb.
	
To comply with Protocol Amendment 4.
 
Not applicable any more.
 
To comply with the protocol.
 
To comply with Protocol Amendment 4.
 
To provide sensitivity analysis.
 
New CaPS format doesn't allow summary of these populations.
 
To provide more detailed analysis.

2. INTRODUCTION

PF 06741086 is a human monoclonal immunoglobulin of the G isotype, subclass 1 (IgG1) that targets the Kunitz 2 domain of tissue factor pathway inhibitor (TFPI). PF 06741086 is in development as a prophylactic treatment to prevent or reduce the frequency of bleeding episodes in individuals with severe hemophilia A or B.

Protocol B7841002 is a first-in-patients safety and pharmacology study with PF 06741086. This study will provide the initial clinical assessment of the safety, tolerability, pharmacokinetics (PK) and pharmacodynamics (PD) of PF 06741086 following administration of subcutaneous (SC) or intravenous (IV) doses at ascending dose levels. Data on bleeding events will be collected to evaluate the therapeutic efficacy of PF-06741086. Study B7841002 will also assess the effect of PF 06741086 on various measures of coagulation. Satisfactory safety, tolerability, PK and PD data from this study are intended to support the development of PF 06741086 as a prophylactic treatment in hemophilia.

This SAP provides the detailed methodology for summary and statistical analyses of the data collected in study B7841002. This document may modify the plans outlined in the protocol; however, any major modifications of the primary endpoint definition or its analysis will also be reflected in a protocol amendment.

2.1. Study Objectives

2.1.1. Primary Objectives:

- *To determine the safety and tolerability of multiple doses of PF-06741086 administered to severe hemophilia A and B subjects with and without inhibitors against FVIII and FIX.*

2.1.2. Key Secondary Objective

- *To assess the clinical efficacy of repeat dosing of PF-06741086.*

2.1.3. Secondary Objectives

- *To characterize the PK profile of PF-06741086.*
- *To characterize the PD profile of PF-06741086.*
- *To characterize the immunogenicity of PF-06741086.*

[figure not shown]
CCI

2.2. Study Design

B7841002 will be an open-label investigation of the safety, tolerability, PK, PD, and efficacy of multiple SC or IV doses of PF-06741086 in males with severe hemophilia A or B. The subjects, investigator, site personnel, and Sponsor will not be blinded to the treatment assignment.

The following schematic is meant to demonstrate the planned dose escalation scenario:

Figure 1. Dose Escalation Scheme

SC/IV multiple dose cohorts will be enrolled in a dose-escalating fashion starting at the 300 mg SC dose. Subjects will be enrolled and assigned to treatment as follows:

- Cohort 1 (n=6): 300 mg PF-06741086 SC QW (n=6);
- Cohort 2 (n=6): 300 mg SC loading dose, 150 mg PF-06741086 SC QW (n=6);
- Cohort 3 (n=6): 450 mg PF-06741086 SC QW (n=6);
- Cohort 4 (n=6): 1000 mg PF-06741086 IV QM (n=6).

Doses, frequency and route(s) of administration after the first dose may be modified based on review of available data. Additional cohorts may be added for reasons described in protocol Section 3.1.

Approximately 24 subjects are planned for enrollment at up to approximately 20 study sites. Subjects who are withdrawn for reasons other than safety may be replaced at the discretion of the Sponsor. Subjects with inhibitors to FVIII or FIX will be enrolled into cohorts currently open for enrollment. Additional subjects and/or cohorts may be enrolled in the event that the number of dosing cohorts or size of dosing cohorts is increased to fully define the dose range and/or clinical profile at the respective dose levels.

3. ENDPOINTS AND BASELINE VARIABLES: DEFINITIONS AND CONVENTIONS

3.1. Primary Endpoints

- *Frequency, severity and causal relationship of treatment emergent adverse events (AEs) (treatment emergent adverse events [TEAEs]) and withdrawals due to TEAEs; Day 1 up to Day 113.*
- *Frequency and magnitude of abnormal laboratory findings (including hematology, PT/INR, aPTT, chemistry, urinalysis, fibrinogen, anti-thrombin III activity and cardiac troponin I); Day 1 up to Day 113.*
- *Changes from baseline in vital sign (blood pressure, pulse rate, temperature and respiration rate) measurements 12-lead electrocardiogram (ECG) parameters and physical examination; Day 1 up to Day 113.*
- *Frequency, severity and casual relationship of infusion and injection site reactions; Day 1 up to Day 113.*

3.1.1. Adverse Events

Any events occurring following start of treatment or increasing in severity will be counted as treatment emergent.

Events that occur in a non-treatment period (applies to screening only) will not be counted as treatment emergent as this is a single-period study.

